## List of Abbreviations

### LIST OF ABBREVIATIONS

AE	Adverse Event/Adverse Experience
CFR	Code of Federal Regulations
CRF	Case Report Form
DSMB	Data and Safety Monitoring Board
FDA	Food and Drug Administration
GCP	Good Clinical Practice
HIPAA	Health Insurance Portability and Accountability Act
IB	Investigator's Brochure
IND	Investigational New Drug Application
IRB	Institutional Review Board
PHI	Protected Health Information
PI	Principal Investigator
SAE	Serious Adverse Event/Serious Adverse Experience
SOP	Standard Operating Procedure
LPP	Lichen Planopilaris
FAA	Frontal Fibrosing Alopecia
MF	Mycosis Fungoides

**Study Summary**

Title	Valchlor in the Treatment of Lichen Planopilaris: A Single Arm, Open-Label, Exploratory Study
Running Title	Valchlor in the treatment of Lichen Planopilaris
Protocol Number	16-006731
Phase	Pilot Study
Methodology	Open-Label, Exploratory Study
Overall Study Duration	14 Months
Subject Participation Duration	6 months
Single or Multi-Site	Single
Objectives	To investigate the efficacy of Valchlor in the treatment of LPP.
Number of Subjects	20
Diagnosis and Main Inclusion Criteria	Adults patient with active LPP or FFA 1) 18 years old or older at time of consent 2) Biopsy proven diagnosis of LPP or FAA
Study Product, Dose, Route, Regimen	Valchlor gel, average use one 60 gram tube per month
Duration of Administration	6 months
Reference therapy	Valchlor gel
Statistical Methodology	The primary endpoint for this study is the LPPAI score. While a minimal clinically significant difference for this outcome measure has not been established, clinically meaningful treatment responses will generate large changes in the LPPAI score given the weightings used in the underlying formula. Therefore, the proposed accrual target of twenty patients will be adequate for the preliminary data generating purposes of an exploratory study.

## 1 Introduction

This document is a protocol for a human research study. This study will be carried out in accordance with the protocol, Good Clinical Practice standards, and applicable United States government regulations and Mayo Clinic research policies and procedures.

### 1.1 Background

Lichen Planopilaris (LPP) is a form of lymphocyte mediated scarring alopecia. It is a chronic condition that predominates in women between the ages of 45-70. Patients present with discrete patches of hair loss with characteristic perifollicular erythema and scale [1]. Diffuse or localized scalp involvement may be seen. Disease progression results in irreversible hair loss and has been associated with significant impact on quality of life, depression, and anxiety [2]. Successful treatment of LPP requires clearance of the lymphocytic inflammation early in the disease course to prevent irreversible follicular destruction and permanent hair loss.

Conventional topical (e.g. corticosteroids) and systemic immunosuppressives (e.g. mycophenolate mofetil) used in the treatment of LPP directly inhibit lymphocytes but generally cannot induce clinical remission [3]. Therefore, there remains a critical unmet therapeutic need for an alternative topical product to treat LPP.

### 1.2 Investigational Agent

Valchlor, a gel formulation of mechlorethamine, is an alkylating agent with anti-neoplastic and anti-inflammatory properties. Each tube of Valchlor contains 0.016% of mechlorethamine which is equivalent to 0.02% mechlorethamine HCL. It is designed for topical application to non-mucosal skin surfaces. With topical administration, there is no systemic absorption. Valchlor is FDA approved for the topical treatment of Stage IA and IB mycosis fungoides (MF) type cutaneous T cell lymphoma in patients who have received prior skin-directed therapy.

### 1.3 Preclinical Data

Valchlor induces lymphocyte apoptosis through either direct cytotoxic effects or possibly through indirect alterations of the surrounding cytokine milieu. This has been demonstrated for neoplastic conditions such as mycosis fungoides as well as for other inflammatory skin disorders such as psoriasis [4,5]. Histologically, the lymphocytic inflammation in LPP is confined to the upper portion of the hair follicle known as the infundibulum. The superficial nature of this lymphocytic inflammation is ideally suited to targeted topical treatment and is also compatible with the absorption and penetration kinetics of Valchlor. The gel vehicle of Valchlor is also especially ideal for hair bearing scalp application. The distribution of Langerhans cells in the hair follicle is greatest in the infundibulum which also corresponds to where the lymphocytic inflammation in LPP is the greatest [6]. Valchlor has been shown to deplete resident Langerhans cells in the epidermis and has been previously reported to clear cutaneous lesions in Langerhans cell histiocytosis [7]. The failure of other systemic immunosuppressives in treating LPP may

reflect the fact that none of these agents directly target Langerhans cells, which constitute the main resident population of antigen presenting cells in both the epidermis and hair follicles and likely are a relevant therapeutic target in the treatment of LPP. Therefore, the multifactorial effects of lymphocyte depletion, Langerhans cell death, and cytokine expression alteration induced by Valchlor warrant investigation of the therapeutic potential of Valchlor in the management of LPP.

#### **1.4 Clinical Data to Date**

There is no clinical research data regarding the efficacy of Valchlor in the treatment of LPP.

#### **1.5 Dose Rationale**

The lymphocyte depleting properties of mechlorethamine, the active ingredient of Valchlor, have been clinically demonstrated with once daily application in the treatment of other skin disorders. The gel delivery vehicle produces immediate liquefaction and rapid drying upon contact which is ideal in the hair bearing scalp and helps to ensure application is restricted to the applied area.

#### **1.6 Risks and Benefits**

The postulated benefits of Valchlor include immunomodulatory effects to induce clinical remission through local effects on lymphocyte proliferation and Langerhans cell function. These benefits will occur without the toxicities associated with systemic immunosuppression, and without the dose-limiting effect of epidermal and dermal atrophy seen with daily high potency topical corticosteroid use.

The possible risks associated with Valchlor include:

1. Flammable Gel. The gel formulation is an alcohol-based product and is flammable when exposed to fire or other flame before completely drying. This risk will be minimized through application instruction procedures provided to study participants and the exclusion of smokers in the study.
2. Embryo-fetal Toxicity. Toxicity has been demonstrated with systemic administration of mechlorethamine, the active ingredient of Valchlor gel. This risk is minimized in that topical application of Valchlor is not associated with detectable levels systemic absorption. Additionally, pregnant, nursing females, or females planning or actively trying to become pregnant will be excluded from the study. All female study participants of child bearing potential prior will be screened for pregnancy with urine B-HCG testing at all study visits and will be required to use one form of contraception during the study period.
3. Non-Melanoma Skin Cancer. Retrospective analysis has shown that 2% (3/128) of patients receiving Valchlor for the treatment of early stage MF developed non-melanoma skin cancer after one year of use. Many of these patients had previously received other treatments known to increase skin cancer risk, and thus the absolute risk directly attributable to Valchlor has not been established. This risk will be minimized in this study in that patients will have surveillance skin

screening at each follow-up visits, a shorter 6 month treatment interval, and once daily application versus the BID to TID application utilized in patients with MF.

4. Mucosal or Eye Injury. Mechlorethamine, the active ingredient in Valchlor, can cause pain, burns, inflammation, photophobia, and blurred vision. Blindness and severe irreversible anterior eye injury may also occur. These risks are highly dependent on both the mechlorethamine concentration and delivery vehicle. For this study, the Valchlor formulation of mechlorethamine at 0.016% in a gel vehicle would be expected to result in mild irritant reactions characterized by erythema or tearing in cases of accidental ocular and/or mucosal exposure. The concentrations producing scarring conjunctivitis or skin vesiculation have been reported to be 1% or higher and are far outside the range of concentrations used for medical purposes [8, 9]. Additionally, there are no reports in the indexed PubMed literature of mucosal blistering, cutaneous blistering/scarring, or permanent ocular injury including blindness with medical range concentrations of Mechlorethamine. Mechlorethamine is used in clinical practice in the United States for face and scalp site application. In mycosis fungoides, especially the folliculotropic variant, multiple case reports have described the use of mechlorethamine application to the face and scalp either as a single agent or in combination with high potency corticosteroids with excellent tolerability and no adverse mucosal or ocular events [10]. Mechlorethamine application to the scalp for Langerhans histiocytosis has also been reported as safe and effective in both the pediatric and adult literature [11]. The risk of the mucosal/eye injury is minimized in this study given the low concentration of Mechlorethamine utilized; additionally, study participants must demonstrate understanding and have the functional capacity to apply the topical Valchlor as directed to be enrolled in the study.

5. Dermatitis. Mechlorethamine in liquid, ointment, cream, and gel formation can induce an idiosyncratic contact dermatitis producing erythema, pruritus, and scaling to areas of application. This is highly treatment responsive to topical corticosteroids and resolves with discontinuation of topical application. This risk is minimized in that Valchlor with a gel vehicle has the lowest incidence of contact dermatitis of any medical grade formulation and that discontinuation of the Valchlor use also results in resolution of the dermatitis.

## 2 Study Objectives

The primary objective of this study is to assess the potential effectiveness of once daily application of Valchlor in decreasing disease activity in patients with Lichen Planopilaris. The primary measurement of efficacy will be with the Lichen Planopilaris Activity Index (LPPAI) before and after 6 months of treatment. Secondary measures of efficacy will be the mean follicular density, Physician Global assessment (PGA) score, and the Dermatology Quality of Life Index (DQLI) score before and after six months of therapy.

### **3 Study Design**

#### **3.1 General Description**

This is a single arm, open label, exploratory study to evaluate the efficacy of Valchlor in the treatment of LPP. Subjects will be screened by the Department of Dermatology at the Mayo Clinic in Florida outpatient clinic and interested qualified subjects will be consented and offered participation. This study is designed to establish feasibility and proof of concept and will not include randomization or crossover components.

Patients with biopsy proven LPP who have failed one prior topical or systemic therapy with evidence of active disease will be eligible to participate. The presence of active disease will be based on a baseline clinical exam showing perifollicular erythema with scaling. Patients with predominance of end stage scarring hair loss but without significant active erythema will be excluded. Involvement restricted to the frontal scalp is a recognized clinical variant of LPP and is known as frontal fibrosing alopecia (FAA). As the histological features of LPP and FAA are identical, patients with FAA subtype of LPP would also be eligible to participate in the study.

Eligible participants using high-potency topical corticosteroids, intralesional corticosteroids, or oral hydroxychloroquine may enroll but will be required to discontinue use during the study period.

All study participants will apply Valchlor 0.016% gel to involved areas at night, beginning with three times a week (Mondays, Wednesdays and Fridays) and increasing to daily application after one month, if well tolerated. Patients will be instructed to first part the hair away from involved area as needed, limit application to areas with alopecia and erythema, apply 30 minutes after showering or washing, and allow treated areas to dry for 5 to 10 minutes before covering with clothing or going to bed. Participants will be instructed to wash their hands with soap and water after applying Valchlor. Caregivers who assist in application will be instructed to wear disposable nitrile gloves when applying Valchlor and dispose with the household trash. Patients will be instructed to store Valchlor in the refrigerator away from foods at 36°F - 46°F and apply within 30 minutes after removing from refrigeration.

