### 3.4 Primary Study Endpoints

The primary outcome measure of efficacy will be the percent reduction of baseline Lichen Planopilaris Activity Index (LLPAI) score after 6 months of treatment defined as follows.

- Complete response: LLPAI reduction greater than 85% from baseline score.
- Partial response: LLPAI reduction of between 25-85% from baseline score.
- Non-response: LLPAI reduction of less than 25% from baseline score.

The Lichen Planopilaris Activity Index (LPPAI) is a standardized validated quantitative measure of disease activity [12]. LPPAI score (0-10) is calculated as follows: (pruritus + pain + burning)/3 + (scalp erythema + perifollicular erythema + perifollicular scale)/3 + 2.5 (pull test) + 1.5 (spreading/2). Symptoms and signs are graded on a 4-point scale with 0 = absent, 1 = mild, 2 = moderate, and 3 =severe. Clinical progression and a positive hair pull test are graded 1=yes; 0=no.

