### 3.5 Secondary Study Endpoints

The secondary outcome measures of efficacy at baseline and after 6 months of treatment will include:

- Mean follicular density as assessed using Canfield scalp photography
- Dermatology Quality of Life Index (DQLI) score : 10 standardized items measuring impact of skin disease rated as 0=not at all/not relevant; 1=a little; 2=a lot; 3=very much
- Physician Global Assessment (PGA) score : using standardized photography compared to the presenting baseline and scored as -1 = worse (no change to erythema with new areas of alopecia); 0 = no change; 1 = mild improvement (slight reduction in erythema, alopecia not progressive); 2= moderate (moderate reduction in erythema, alopecia not progressive); 3 = significant improvement (very mild erythema, alopecia not progressive); 4 = clear (no erythema, alopecia not progressive)

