### 3.6 Primary Safety Endpoints

The primary safety endpoint of this study will be the number of days between unintentional mucosal and/or ocular exposure during the study period.

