## 4.4 Early Withdrawal of Subjects

### 4.4.1 When and How to Withdraw Subjects

Patients are free to withdraw at any time and for whatever reason. No data will be collected for withdrawn subjects and withdrawn subjects may be replaced within the accrual period. There will be no follow-up for withdrawn subjects. Pre-specified reasons for discontinuing include, but are not limited to, the following:

- Patient Request: Patient decided that he/she did not want to continue (for any reason)
- Adverse Event: Patient experienced a related or unrelated event that would interfere with the study objectives/evaluation
- Lost to Follow-up: Patient did not come in for a visit and could not be reached by phone
- Treatment Failure: If in the Principal Investigator and/or Investigators' judgment, the patient's condition required another form of treatment
- Mechlorethamine sensitization: Patient develops contact dermatitis to Valchlor that cannot be managed with low potency topical corticosteroids
- Inclusion/Exclusion Discrepancy/Violation: Patient should not have been enrolled
- Noncompliance: Patient is not complying with the protocol requirements (i.e. visit schedule, dosing, regimen, etc.); a patient is to be withdrawn if he/she misses two consecutive visits
- Other: Any other reason

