## **5.5 Subject Compliance Monitoring**

Study participants will be dispensed one 60 gram tube at the qualifying baseline exam, 2 tubes at week 4 following phone visit, and 3 tubes at the week 12 follow-up visit. They will be instructed to use one tube per 30 days and be will instructed to bring these tubes for all follow-up visits. Weights of each tube after 30 days of use will be recorded.

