## **7 Statistical Plan**

### **7.1 Sample Size Determination**

Due to the pilot nature of the study, no formal statistical power or sample size calculations are necessary. The sample size of 20 patients will be sufficient for this pilot study to obtain a preliminary estimate of treatment efficacy and to generate data that will be useful in the design of a larger study.

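### Feasibility is a stated design purpose, but nothing in the plan estimates it, and the withdrawal and missing-data rules may leave retention and tolerability exits unreported

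*Combined protocol and SAP*

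**What the plan says.** Section 3.1 gives the study two purposes: "This study is designed to establish feasibility and proof of concept and will not include randomization or crossover components". Section 7.1 justifies 20 patients partly by the aim "to generate data that will be useful in the design of a larger study".

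The stated measures are these:

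- Objective (Section 2): "The primary objective of this study is to assess the potential effectiveness of once daily application of Valchlor in decreasing disease activity".
- Primary endpoint (3.4): "The primary outcome measure of efficacy will be the percent reduction of baseline Lichen Planopilaris Activity Index (LLPAI) score after 6 months of treatment".
- Secondary endpoints (3.5): "The secondary outcome measures of efficacy at baseline and after 6 months of treatment will include", followed by follicular density, the dermatology quality-of-life score and the physician global assessment.
- Safety endpoint (3.6): "The primary safety endpoint of this study will be the number of days between unintentional mucosal and/or ocular exposure during the study period".

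On withdrawals, Section 4.4.1 says that no data will be collected for withdrawn participants and, in the same sentence, that "withdrawn subjects may be replaced within the accrual period". It sets no limit on replacements. Section 4.4.2 rules out further contact. Section 7.2 does not impute and leaves missing values missing. Section 7.3 puts every participant who received study drug in the primary analysis whether or not they withdrew, with a secondary analysis that leaves withdrawals out.

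Some relevant data are recorded. On compliance, Section 5.5 says: "Weights of each tube after 30 days of use will be recorded". Section 5.9.3 requires drug reconciliation and Section 8.2 requires recording of all adverse events.

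**The concern.** A pilot that claims to establish feasibility should report whether patients can be recruited, stay to Week 24, tolerate the gel and use it. This plan names none of these as a quantity to estimate, although it relies on them elsewhere. Section 7.2 asserts that accrual is achievable. Section 5.2 makes the step to daily application conditional on tolerance. Section 8.5 allows the study to be stopped for an unexpectedly high incidence of contact dermatitis.

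The withdrawal rules make the gap worse. If leavers are replaced until 20 finish, and little or nothing is recorded about those who left, the team planning the next study could have a response rate but no dependable retention or tolerability figure to go with it.

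**Working it through.** **Step 1. Look for a planned feasibility estimate.**

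| Feasibility question | Data in the plan | Planned endpoint or analysis |
|---|---|---|
| Retention to Week 24 | Visit attendance (Section 6) | None |
| Exits for dermatitis or other adverse events | Adverse events recorded (8.2); withdrawal reasons listed (4.4.1), but recording them is not required there | None |
| Adherence | Tube weights (5.5), reconciliation (5.9.3), compliance review at Week 12 (Section 6) | None |
| Recruitment rate | Consent at Visit 1; enrolment date not in the source-data list (3.7) | None |

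Section 7.2 has a general rule for summarising continuous and categorical variables, but does not say that any of these will be summarised.

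**Step 2. Read the withdrawal rules together.** Under 7.3 a treated participant who withdraws is in the primary analysis set. Under 4.4.1 and 4.4.2 no data are collected for that person and no contact is made, so there is no Week 24 LPPAI. Under 7.2 the missing value stays missing, and the plan does not assign withdrawals to non-response. The person therefore counts in the analysis set but contributes nothing to the percent reduction at 6 months. In practice the estimate may rest on completers only.

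**Step 3. Size, as an illustration.**

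*Inputs.* The planned number is 20 (Section 3.2); the data quality check in Section 9.3 also treats 20 as the final count. Section 7.1 says no formal sample size calculation was made, so there is no calculation of the plan's own to reproduce. The documents give no dropout rate d; 10% to 40% is an assumption.

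*Formulas.* Number treated to obtain 20 completers = 20/(1 − d), rounded up. True retention = 20/number treated, with a Clopper-Pearson 95% interval.

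| Assumed d | 20/(1 − d) | Treated | True retention | Exact 95% CI |
|---|---|---|---|---|
| 10% | 22.2 | 23 | 20/23 = 87% | 66-97% |
| 20% | 25.0 | 25 | 20/25 = 80% | 59-93% |
| 30% | 28.6 | 29 | 20/29 = 69% | 49-85% |
| 40% | 33.3 | 34 | 20/34 = 59% | 41-75% |

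Counting only the final 20 gives 20/20 = 100% (83-100%) in every row.

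The same denominators matter for response. With a hypothetical 8 responders, 8/20 = 40% among completers, but 8/25 = 32% over 25 treated if withdrawals count as non-responders.

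**The case against.** The strongest reply is Section 7.3. If 25 are treated and 5 withdraw, its primary set has 25 and its secondary set 20, so the withdrawals are visible. A reader might infer from the replacement rule that the plan removes the true denominator, or will report 20 of 20 completed. The documents do not support that: 7.3 points the other way, and no section says such a figure will be reported. What remains is narrower. Section 7.3 governs the efficacy analysis, plans no completion or exit rate, and sits badly with 4.4.1 and the missing-data rule.

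Section 4.4.1 can also be read mildly, as meaning that nothing further is collected after withdrawal. Section 9.3 requires missing CRF data to be explained, which might capture a reason. On that reading earlier data survive, but the Week 24 score is still absent and no feasibility summary is planned.

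A reader might also infer that withdrawals and their reasons are already collected, so that analysis wording alone would do. Section 4.4.1 lists reasons without requiring that they be recorded, and says no data will be collected for these participants. Tube weights and adverse events are clearly recorded. Final tube weights from those who leave are not assured.

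Lastly, feasibility appears as one word in a protocol otherwise about efficacy, with no threshold depending on it. That limits the severity. Deleting the word would tidy the text, but would leave the conflict between 4.4.1 and 7.3, and the next study would still lack these figures.

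**Conclusion.** The point holds in this form. Feasibility is one of two stated design purposes, and the plan followed literally cannot support a conclusion about it. The withdrawal, follow-up and missing-data rules together create a risk, not a certainty, that retention and tolerability exits go unreported and that efficacy results reduce to completers.

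The size depends wholly on an assumed dropout rate. Over 10% to 40%, true retention behind 20 completers runs from 87% to 59%. It also assumes that leavers are replaced until 20 finish, which 4.4.1 permits but does not require. The change should be made, but the matter is moderate for an exploratory single-arm pilot, and no error rate or power figure is affected.

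**What to change.** 1. Amend 4.4.1 so that the date of and reason for withdrawal, and all data obtained up to withdrawal, are recorded and kept for everyone treated. Reconcile it with 7.3, stating how a participant without a Week 24 LPPAI enters the primary analysis.
2. Add to 3.5 and 7.2 one descriptive table over all participants ever treated, replaced ones included:
   - proportion completing Week 24, with an exact 95% CI;
   - proportions leaving for contact dermatitis and for any adverse event, each with an exact 95% CI;
   - gel use from the available tube weights, stating how many participants contribute;
   - participants enrolled per month, with the enrolment date recorded.

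This needs no new visit, procedure or increase in sample size. The cost is a protocol amendment, minor extra recording at withdrawal and one table. The completion figure may look less favourable than a count of the final 20.
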